## Section 4: Statistical Principles

**4.1. Level of statistical significance:** see above description of p-value for interim analyses.

**4.2. Description and rationale for any adjustment for multiplicity of time points:** There will be no adjustment for multiple outcomes, as all were pre-planned. The investigator-statistician in charge ([name]) strongly agrees with the argument that adjustment for multiple comparisons in pre-planned hypotheses leads to more type II errors.

**4.3. Analysis populations:** all analyses, including safety analyses, will be conducted initially as **intention-to-treat** and then **as-treated**.

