- INR > 1.7 (with or without concurrent use of warfarin)
- Platelet count < 100 x 10⁹/L or history of HITT
- Fibrinogen < 300mg/dL
- Known abdominal or thoracic aneurysm
- History of CNS malignancy or CNS metastasis within past 5 years
- History of non-CNS malignancy within the past 5 years that commonly metastasizes to the brain (lung, breast, melanoma)
- Prisoner status

Patients will be sequentially assigned to one the following three groups as follows:

1. Group tPA50 will receive 50 mg of tPA intravenous bolus administration over 2 hours, given as a 10 mg push followed by the remaining 40 mgs over a total time of 2 hrs (not to exceed 0.9mg/kg dose). Immediately following the tPA infusion, 5000 U of UFH will be delivered and the heparin drip will be continued to maintain the activated partial thromboplastin time at 60-80sec (2.0 to 2.5 times the upper limit of normal). This tPA protocol is a modification of the GUSTO I to III trials.^{45,46}

2. Group tPA50 plus drip will receive 50 mg of tPA intravenous bolus administration over 2 hours, given as a 10 mg push followed by the remaining 40 mgs over a total time of 2 hrs (not to exceed 0.9mg/kg dose). Immediately following this initial tPA infusion, we will initiate a drip of 2 mg/hr tPA over the ensuing 24 hours (total 48 mg infusion) accompanied by an infusion of 500U/hour heparin during the tPA drip. After this, heparin dose will be increased slowly to maintain a PTT between 60 and 80 sec, titrated per attending's discretion.⁴⁷

3. Control: standard of care according to the institution's protocol for ARDS

Amendment Nov 4, 2020: please see below description for more detailed information on adaptation. The rationale for adjusting the tPA administration to a 50 mg bolus followed by a 2mg/hr infusion over the ensuing 24 hr is based on the facts that:

- 1) a convincing improvement in P/F was observed at 24 hr, but was lost over the ensuing 24 hr,
- 2) there was no discernable response to the second tPA bolus at the 24 hr time point,
- 3) we believe the initial 50 mg bolus has provoked fibrinolysis shutdown ;ie, PAI-1 generation in response to the tPA bolus blunting a response to a second bolus at 24 hr,
- 4) an infusion of low dose tPA will consume the PAI-1 generated in response to the initial tPA bolus and provide an additional fibrinolytic intervention over the ensuing 24 hr,

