Additional two tubes (total volume up to 8.0mL) of blood will be drawn at each timepoint to be processed in the research lab.

Thrombo Therapeutics, Inc. is not involved in this study. TPA-challenged TEG assay is used for research purposes only. The data from this test is not accessible for the clinical care providers and

does not affect the patient care. We are using this assay to study the clot sensitivity and as a marker for hypercoagulability. The results of tPA-challenged TEG assay will not be used for any clinical decision or research subject assignment. At the moment there is no plan to submit tPA-challenged TEG data to the FDA.

Follow-up:

Patients will be followed to death or discharge up to 28 days. Laboratory measurements related to the research study, however, will end at day 7 after randomization.

Outcomes:

Primary Outcome: PaO₂/FiO₂ improvement from pre-to-post intervention at 48 hours post randomization. Ideally, the PaO₂/FiO₂ will be measured with the patient in the same prone/supine position as in baseline, as change in positions may artificially reduce the improvement attributable to the study drug. However, given the pragmatic nature of the trial, the prone/supine position will be determined by the attending physician, in which case, we will use as an outcome the PaO₂/FiO₂ closest to the 48 hours obtained prior to the change in position as the outcome.

Secondary outcomes (assessed 48 hours after randomization or as indicated):

- PaO₂/FiO₂ improvement from pre-to-post intervention at **24 hours** post randomization.
- Amendment Nov 5, 2020: add the outcome "Decrease in ventilatory dead space as estimated by the ventilatory ratio at **48 hours.**" Based on a recent study, (Orfanos S, El Hussein I, Nahass T, et al. Observational study of the use of recombinant tissue-type plasminogen activator in COVID-19 shows a decrease in physiological dead space. ERJ Open Res 2020; 6: 00455-2020), this outcome seems to appropriate to assess the efficacy of the intervention. As most of the subjects do not have capnography data, we will be using the ventilatory ratio, which has been shown to correlate well with dead space.
- Achievement of PaO₂/FiO₂ ≥ 200 or 50% increase in PaO₂/FiO₂ (whatever is lower)
- National Early Warning Score (NEWS2): based on 7 clinical variables (respiration rate, oxygen saturation, any supplemental oxygen, temperature, systolic blood pressure, heart rate, level of consciousness).

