**2. SAP version 4, 11/30/2020**

### **Section 2: Introduction**

#### **2.1. Synopsis of trial background and rationale**

Similar to pathologic findings of ARDS, microthrombi have now been observed in lung specimens from patients infected with COVID-19 . Generalized derangements of the hemostatic system with prolongation of the prothrombin time, reduced prothrombin time activity, and elevated D-dimer and fibrin degradation products have been reported in severely ill COVID-19 patients, particularly in non-survivors . These laboratory findings, in combination with the large clot burden seen in the pulmonary microvasculature, mirrors that seen in human sepsis , experimental endotoxemia , and massive tissue trauma . Targeting the coagulation and fibrinolytic systems to improve the treatment of ARDS has been proposed for at least the past two decades . In particular, the use of plasminogen activators to limit ARDS progression and reduce ARDS-induced death has received strong support from animal models , and a phase 1 human clinical trial . In 2001, Hardaway and colleagues  showed that administration of either urokinase or streptokinase to patients with terminal ARDS reduced the expected mortality from 100% to 70% with no adverse bleeding events.

Tissue plasminogen activator (alteplase) is a more modern approach to fibrinolysis, for which there is extensive experience in myocardial infarction, stroke and major pulmonary embolism . Most current trials included in clinicaltrials.gov for the COVID-19-induced SARS aim at modulating the inflammatory response or test anti-viral drugs. Sarilumab and tocilizumab that block IL-6 effects are being tested in RCT for patients hospitalized with severe COVID-19 (NCT04317092, NCT04322773, NCT04327388). The World Health Organization international trial SOLIDARITY will test remdesivir; chloroquine + hydroxychloroquine; lopinavir + ritonavir; and lopinavir + ritonavir and interferon-beta (NCT04321616). Yet studies targeting the coagulation system, which is intrinsically intertwined with the inflammatory response are lacking. 

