### **Secondary outcomes (assessed 48 hours after randomization or as indicated)**

- Per amendment after first interim analysis Nov 5, 2020, we added two secondary outcomes:
- PaO2/FiO2 improvement from pre-to-post intervention at 24 hours post randomization.
- Amendment Nov 5, 2020: add the outcome "Decrease in ventilatory dead space as estimated by the ventilatory ratio at 48 hours." Based on a recent study, (Orfanos S, El Hussein I, Nahass T, et al. Observational study of the use of recombinant tissue-type plasminogen activator in COVID-19 shows a decrease in physiological dead space. ERJ Open Res 2020; 6: 00455-2020), this outcome seems to appropriate to assess the efficacy of the intervention. As most of the subjects do not have capnography data, we will be using the ventilatory ratio, which has been shown to correlate well with dead space.
- Achievement of PaO2/FiO2 ≥ 200 or 50% increase in PaO2/FiO2 (whatever is lower)
- National Early Warning Score (NEWS2): based on 7 clinical variables (respiration rate, oxygen saturation, any supplemental oxygen, temperature, systolic blood pressure, heart rate, level of consciousness).
- NIAID ordinal scale: The ordinal scale is an assessment of the clinical status as follows: 1) Death; 2) Hospitalized, on invasive mechanical ventilation or extracorporeal membrane oxygenation (ECMO); 3) Hospitalized, on non-invasive ventilation or high flow oxygen devices; 4) Hospitalized, requiring supplemental oxygen; 5) Hospitalized, not requiring supplemental oxygen - requiring ongoing medical care (COVID-19 related or otherwise); 6) Hospitalized, not requiring supplemental oxygen - no longer requires ongoing medical care; 7) Not hospitalized, limitation on activities and/or requiring home oxygen; 8) Not hospitalized, no limitations on activities. (combined items 7 and 8 as our study is limited to hospital)
- 48 hour in-hospital mortality

- 14 days in-hospital mortality
- 28 days in-hospital mortality
- ICU-free days (up to 28 days)
- In-hospital Coagulation-related event-free (arterial and venous) days (up to 28 days)
- Ventilator-free days (up to 28 days)
- Successful extubation (no re-intubation for >3 days after initial extubation)
- Successful weaning from paralysis for > 3 days after initial termination
- Survival to discharge

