### Section 3: Study Methods

**3.1. Trial design** Multicenter, pragmatic, randomized, open label, rapidly adaptive, controlled, clinical trial

The trial has a novel design with modified stepped-wedge and adaptive features in order to rapidly identify the intervention group with the highest chance of benefit. This unconventional design is appropriate for the current circumstances of the pandemic caused by a new, lethal and morbid virus infection (COVID-19) for which no known treatment exists. The below figure illustrates the design. In brief, the patients will be sequentially assigned to one of three following groups:

[figure not shown]
[figure not shown]
- Group tPA50 will receive 50 mg of tPA intravenous bolus administration over 2 hours, given as a 10 mg push followed by the remaining 40 mgs over a total time of 2 hrs (not to exceed 0.9mg/kg dose). Immediately following the tPA infusion, 5000 U of UFH will be delivered and the heparin drip will be continued to maintain the activated partial thromboplastin time at 60-80sec (2.0 to 2.5 times the upper limit of normal). This tPA protocol is a modification of the GUSTO I to III trials. 44,45
- Group tPA50 plus drip will receive 50 mg of tPA intravenous bolus administration over 2 hours, given as a 10 mg push followed by the remaining 40 mgs over a total time of 2 hrs (not to exceed 0.9mg/kg dose). Immediately following this initial tPA infusion, we will initiate a drip of 2 mg/hr tPA over the ensuing 24 hours (total 48 mg infusion) accompanied by an infusion of 500 U/hr heparin during the tPA drip. After this, heparin dose will be increased slowly to maintain a PTT between 60 and 80 sec, titrated per attending's discretion.
- Control: institution's protocol for ARDS

In order to rapidly accrue patients in one intervention group with a concurrent control, the first 10 patients will be randomly assigned to Group tPA50 or Control (Standard-of-care) when the first interim analysis occurs. If no stopping criteria are met, the next 10 patients are randomly

assigned to Group tPA50 or Control when the second interim analysis is done. If no criteria for stopping or dropping an arm are met, the next 10 patients are randomly assigned to Group tPA50 plus drip or Control when the third interim analysis is done. Finally, if no criteria for stopping or dropping an arm are met, the trial progresses with patients being randomized to Group tPA50 plus drip or Control up to the final analysis at n=50.

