### 3.3. Statistical interim analyses and stopping guidance:

#### ***Criteria for stopping the clinical trial early for efficacy or harm:***

Stopping the clinical trial early for efficacy or harm
Reaching adjusted p-value for the primary outcome and at least one of the secondary outcomes at all follow-up time points
DSMB deemed harm profile unacceptable

**Criteria for stopping for futility:** we will follow the guidelines established by Jitlal et al :

Stopping the clinical trial early for futility
•Low conditional power ( $\leq 15\%$ ), calculated using PASS 14 with bootstrapping simulations, based on the target minimum differences for all primary and secondary outcomes at all follow-up time points.
•Observed difference size in the primary or secondary outcomes favor the control group ( $< 5\%$ ) at all follow-up time points.
•The DSMB and trial team agree that enough patients and events have been observed so far to produce a reliable effect
•There are less than 2 centers interested in continuing enrollment
•There is no evidence of an effect in any pre-specified subgroups.
•The DSMB deemed the adverse events profile acceptable (if there are no safety concerns, we may wish to continue to ensure that a modest effect is not missed).

**3.4. Adaptive design:** The study interim analyses will be used to propose pre-planned modifications based on observed effects, recruitment, eligibility and other aspects of the study as determined below.

- Drop/add study arms: deploying study arms sequentially (vs in-parallel) allows sufficient sample sizes in each arm to assess outcomes and adverse events. Study arms that show significant improvement may ethically preclude the deployment of other arms. Similarly, study arms which show adverse events (as listed) attributable to the intervention (per trial team with DSMB /IRB determination) or minimal/no improvement may be eliminated. Study arms may be added if concurrent trials demonstrate significant evidence of benefit of a different route, dose, mode of administration of the study drugs.

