### 6.5. Pre-planned subgroup analyses

We anticipate the following subgroup analyses, which will assist in determining whether there is a subgroup of patients for whom the intervention is more beneficial/harmful.

- Baseline PaO2/FiO2 <100 and <50
- Hemodynamic instability with vasopressors
- Age <35, <50, <65 years
- D-Dimers median levels
- Fibrinolysis shutdown (by TEG or ROTEM)
- Fibrinogen median levels
- Prone/supine positioning
- Requirement of re-bolusing of alteplase
- Received dose of alteplase as premature death or adverse event or other reasons may preclude the administration of complete treatment
- Elimination of centers contributing <2 cases.

Additional subgroup analyses may be defined at an interim analysis and will be added for the subsequent interim analyses. This will be documented by filing another version of this SAP with the IRBs, DSMB, funder and FDA.

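### The multiplicity waiver rests on all outcomes being pre-planned, but 24-hour P/F and ventilatory ratio were added after the first interim analysis

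*SAP*

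**What the plan says.** SAP 4.2 states: "There will be no adjustment for multiple outcomes, as all were pre-planned". It supports this with an argument that is itself limited to pre-planned hypotheses. The protocol repeats the sentence at the end of its statistical analysis section.

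The secondary outcome list in SAP 2.2 opens differently: "Per amendment after first interim analysis Nov 5, 2020, we added two secondary outcomes". The two are P/F improvement at 24 hours and ventilatory ratio at 48 hours. The document is headed "SAP version 4, 11/30/2020", so it postdates the amendment and still carries the waiver.

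The protocol's outcome list marks only ventilatory ratio, with the words "Amendment Nov 5, 2020: add the outcome". It lists 24-hour P/F without any mark. Elsewhere, in the dosing rationale headed November 4, 2020, the protocol records that "a convincing improvement in P/F was observed at 24 hr, but was lost over the ensuing 24 hr".

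**The concern.** A reader of SAP 4.2 is told that every outcome was fixed in advance. For two of them the SAP itself says otherwise. For 24-hour P/F this is more than a label, because 24-hour results had been seen when it became an outcome. The same patients stay in its later tests: the looks in the SAP sample size table are cumulative (10, 20, 30, 50), SAP 6.4 analyses by intention to treat, and no passage sets the first 10 patients aside. At stake is how much weight a nominally significant 24-hour P/F result can bear.

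**Working it through.** **Step 1. Is adding outcomes a planned adaptation?** SAP 3.4 says the interim analyses will be used to "propose pre-planned modifications based on observed effects, recruitment, eligibility and other aspects of the study as determined below". The items that follow, in the SAP and the protocol, are arms, entry criteria, sample size, cessation rules, enrollment and refusal, crossover, positioning, and dose, duration or mode of administration. Outcomes are not among them. SAP 6.5 does provide for later additions, but of another kind: "Additional subgroup analyses may be defined at an interim analysis and will be added for the subsequent interim analyses". So the adaptive plan does not make the two outcomes pre-planned.

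**Step 2. What was known at the time?** The 24-hour observation is dated November 4 and the outcome amendment November 5. I read the observation as coming from the first interim analysis, planned at 10 patients. This is an inference from the dates and from the November 5 amendment, which cites that analysis. No first-look statistic is given, and the text does not say whether the improvement was within the tPA group or against control. For ventilatory ratio, SAP 2.2 cites an external study and reports no interim result.

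**Step 3. How much could it matter?** The plan gives no figure, so this is a conditional illustration. It applies only if the outcome was added because the first-look z exceeded c.

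Inputs:
- From the SAP: boundary b = 2.39658 at n = 50, two-sided nominal level 2 × [1 − Φ(2.39658)] = 1.65%.
- Assumed: 1:1 allocation (5 v 5 at look 1, 25 v 25 at the end), equal variances, no true effect, normal approximation, c from 0.5 to 1.96.

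Correlation ρ between the first-look z and the final pooled z:
- Between-group signal: ρ = √(5/25) = 0.447.
- Within-tPA signal: ρ = 0.447/√2 = 0.316.

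Error = P(|Z| > b | Z1 > c) = [1/(1 − Φ(c))] × ∫ from c to ∞ of φ(z) × {1 − Φ[(b − ρz)/√(1 − ρ²)] + Φ[(−b − ρz)/√(1 − ρ²)]} dz.

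| c | 0.5 | 1.0 | 1.28 | 1.645 | 1.96 |
|---|---|---|---|---|---|
| Between groups | 2.2% | 3.1% | 3.9% | 5.3% | 6.8% |
| Within tPA, no mean change | 1.9% | 2.4% | 2.8% | 3.5% | 4.2% |

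Entry requires P/F below 150, so P/F may rise in both arms without a drug effect. If a shared upward drift gives the within-group first-look z a mean of 1 to 2 standard errors, c is replaced by c minus that mean in the formula. The error is then about 1.5 to 2.4%, close to nominal.

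**Step 4. What does leaving out the first 10 patients cost?** Under SAP 3.1 the first two stages randomize to tPA50 or control. After that, "the next 10 patients are randomly assigned to Group tPA50 plus drip or Control when the third interim analysis is done", and the drip continues to n = 50. With 1:1 allocation this gives 10 tPA50, 15 drip and 25 controls. Removing the first 10 patients leaves 5, 15 and 20, so tPA50:drip moves from 10:15 to 5:15.
- Interval width: √(50/40) = 1.118, about 12% wider.
- A test with 80% power at critical value 1.96: Φ[(1.96 + 0.84) × √0.8 − 1.96] = 0.71.
- The same at 2.397: Φ[(2.397 + 0.842) × √0.8 − 2.397] = 0.69.

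The documents state no power for 24-hour P/F, so the 80% is only a reference point.

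**The case against.** **The additions are disclosed and little depends on them.** SAP 2.2 announces them, SAP 3.2 promises effect sizes with intervals and disowns a rigid cutoff, and unadjusted secondary outcomes are acceptable in an open-label Phase 2a trial. This stands. The number of outcomes is not the issue either. Going from 12 to 14 moves the chance of at least one false positive, if independent and each tested at 5%, only from 1 − 0.95^12 = 46.0% to 1 − 0.95^14 = 51.2%. What fails is the stated reason for the waiver.

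**24-hour P/F was already in the design.** Blood gases at hour 24 were scheduled and the re-bolus rule uses 24-hour P/F. That makes it a planned measurement. It does not make it a planned efficacy outcome, and SAP 2.2 itself says it was added.

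**The error rates are conditional.** This stands. Any outcome, even a properly pre-specified one, shows the same arithmetic after a favourable first look. The figures count as an error of the plan only if the result led to the addition. A reader might infer that it did, but the documents show only the order in time. They present the 24-hour observation as a reason for changing the dosing.

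**The efficacy stop.** A reader might infer that 24-hour P/F makes a false early stop more likely. SAP 3.3 requires the primary outcome to reach its adjusted p-value as well. A secondary outcome therefore cannot raise the rule's type I error above that of the primary's own boundary.

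**Conclusion.** The contradiction is real and lies within current text: the waiver's premise is false for two of the 14 listed secondary outcomes.

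For 24-hour P/F it limits what the trial can claim. If a between-group first-look result prompted the addition, the final pooled test carries about 2.2 to 6.8% error against a nominal 1.65%. If the signal was within the tPA group, the figure is 1.9 to 4.2% with no mean change and about 1.5 to 2.4% with a shared drift of 1 to 2 standard errors. These ranges rest on an assumed range for the first-look z, which the documents do not give, and on a normal approximation with 5 patients per group at that look. The finding itself does not depend on them.

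For ventilatory ratio only the label is shown to be wrong. Nothing supports reading that outcome as driven by trial data. The primary outcome is unaffected. A comparison of the drip arm with its concurrent controls contains no first-look patient and is unaffected too.

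**What to change.** Replace the sentence in SAP 4.2 and in the protocol's statistical analysis section by:

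> No adjustment is made for the secondary outcomes listed before the first interim analysis, which were pre-planned. 24-hour P/F and ventilatory ratio were added after that analysis, are not pre-planned, and are reported unadjusted: 24-hour P/F as exploratory, ventilatory ratio as added after the first interim analysis.

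Then:
- Mark both outcomes as added after the first interim analysis in both outcome lists (SAP 2.2 and the protocol).
- Report 24-hour P/F with effect size and interval for all patients. Add a sensitivity analysis of pooled tPA versus control without the first 10 patients, noting the change in tPA50:drip mix from 10:15 to 5:15.
- Leave the second rule of the November 5 amendment as it is, and state that its 24-hour P/F input includes 10 patients whose 24-hour data had already been seen.
- Make no change to the efficacy stop in SAP 3.3.

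The cost is wording plus one sensitivity analysis with intervals about 12% wider. As an illustration, 80% power in that analysis would become about 71% at 1.96 or 69% at 2.397. Data collection and the primary analysis do not change, and the exploratory all-patient report loses no patients.
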